15.2.2. Part B: Caucasian Participants – SC dose

Procedure	Screening (up to 28 days before Dosing)	Day - 1	Day 1			Days 2-85														Follow Up/Early Withdrawal (112 Days post dose) ³	
			Pre-Dose	0h	Post Dose ¹	2 ²	3 ²	4 ²	6 ²	8	11	15	18	22	29	43	57	71	85		
Window			-60 min							±1d	±2d	±2d	±2d	±2d	±2d	±3d	±3d	±3d	±3d	±7d	
Informed consent	X																				
Inclusion and exclusion criteria	X	X																			
Demography	X																				
Full physical examination including height and weight	X																				X
Medical history (includes substance usage)	X																				
Past and current medical conditions	X																				
Serology (HIV, HBV, HCV, CMV, EBV, VZV)	X																				
TB screening (QuantiFERON ± PPD)	X																				

Procedure	Screening (up to 28 days before Dosing)	Day - 1	Day 1			Days 2-85														Follow Up/Early Withdrawal (112 Days post dose) ³		
			Pre-Dose	0h	Post Dose ¹	2 ²	3 ²	4 ²	6 ²	8	11	15	18	22	29	43	57	71	85			
Window			-60 min							±1d	±2d	±2d	±2d	±2d	±2d	±3d	±3d	±3d	±3d	±3d	±7d	
Breath Alcohol Screen	X	X																				
Urine Drug Screen	X	X																				
Haematology & Clinical Chemistry	X	X				X	X			X		X			X	X	X			X	X	
Urinalysis	X	X				X	X			X		X			X	X	X			X	X	
12-Lead ECG ⁴	X		X		X ⁵	X														X	X	
Vital Signs ⁶	X	X	X		X	X	X	X	X	X	X	X	X	X	X	X	X	X	X	X	X	X
Randomization		X																				
IMP Administration				X ⁷																		
Resident in Unit		<----->																				
Local tolerability at injection sites			X		X ⁸	X		X		X												
sLAG3 concentrations			X			X	X	X	X	X	X	X	X	X	X	X	X	X	X	X	X	X
PK			X			X	X	X	X	X	X	X	X	X	X	X	X	X	X	X	X	X
Immunogenicity			X												X		X			X	X	

Procedure	Screening (up to 28 days before Dosing)	Day - 1	Day 1			Days 2-85														Follow Up/Early Withdrawal (112 Days post dose) ³		
			Pre-Dose	0h	Post Dose ¹	2 ²	3 ²	4 ²	6 ²	8	11	15	18	22	29	43	57	71	85			
Window			-60 min							±1d	±2d	±2d	±2d	±2d	±2d	±2d	±3d	±3d	±3d	±3d	±3d	±7d
LAG3 ⁺ Cell Depletion			X			X		X		X		X			X	X	X			X	X	
Genetic Sample ⁹			X																			
AE/SAE Review	SAEs collected from signing of informed consent form; AEs collected continuously from time of first dose.																					
Concomitant medication review	Monitored from screening until the end of the final treatment period.																					

Footnotes:

1. All post dose time points are in reference to the first injection of IMP.
2. Assessments at these visits should be on the scheduled day however can be at any time in the day.
3. Early withdrawal assessments will be the same as Follow-Up.
4. ECG in triplicate at screening and single at all other time points.
5. ECG to be performed 6 hours post dose.
6. Vital Signs to be taken every 30 minutes from first IMP injection until completion of 2hr post dose monitoring period.
7. IMP administration consists of 3 syringes, all 3 syringes are to be administered as closely together as possible (preferably within 10 minutes).
8. Post dose Local tolerability at injection sites to be reviewed at 2, 6, 12, and 24 hours post dose.
9. The genetic sample is optional and can be taken any time after consent has been signed and the participant is randomized.

15.3. Appendix 3: Assessment Windows

15.3.1. Definitions of Assessment Windows for Analyses

No assessment windows will be defined for analyses. Summaries and analyses will be based on nominal visits.

15.4. Appendix 4: Study Phases and Treatment Emergent Adverse Events

15.4.1. Study Phases for Parts A and B

Assessments and events will be classified according to the time of occurrence relative to the dose.

Study Phase	Definition
Pre-Treatment	Date/Time \leq Study Treatment Start Date/Time
Treatment Emergent	Date/Time $>$ Study Treatment Start Date/Time

15.4.1.1. Study Phases for Concomitant Medication

Study Phase	Definition
Prior	If medication end date is not missing and is prior to study treatment.
Concomitant	Any medication that is not a prior

NOTES:

- Please refer to [Appendix 7: Reporting Standards for Missing Data](#) for handling of missing and partial dates for concomitant medication. Use the rules in this table if concomitant medication date is completely missing.

15.4.2. Treatment Emergent Flag for Adverse Events

Adverse Events will be flagged as Treatment Emergent as described in the table in Section [15.4.1](#), where the AE Start Date/Time will be considered.

15.5. Appendix 5: Data Display Standards & Handling Conventions

15.5.1. Reporting Process

Software	

 The currently supported versions of SAS software will be used. 	
Reporting Area	
HARP Server	: us1salx00259
HARP Compound	Each of the following directories will be used for both Parts A and B. : \arprod\gsk2831781\mid207823\internal_01 : \arprod\gsk2831781\mid207823\interim_01 : \arprod\gsk2831781\mid207823\final_01
Analysis Datasets	

 Analysis datasets will be created according to Integrated Data Standards Library (IDSL) GSK A&R dataset standards. 	
Generation of RTF Files	

 RTF files will be generated for SAC. 	

15.5.2. Reporting Standards

General	

 The current GSK Integrated Data Standards Library (IDSL) will be applied for reporting, unless otherwise stated (IDSL Standards Location: https://spope.gsk.com/sites/IDSLLibrary/SitePages/Home.aspx): 
 4.03 to 4.23: General Principles 5.01 to 5.08: Principles Related to Data Listings 6.01 to 6.11: Principles Related to Summary Tables 7.01 to 7.13: Principles Related to Graphics Do not include participant level listings in the main body of the GSK Clinical Study Report. All participant level listings should be located in the modular appendices as ICH or non-ICH listings. 	
Formats	

 GSK IDSL Statistical Principles (5.03 & 6.06.3) for decimal places (DP's) will be adopted for reporting of data based on the raw data collected, unless otherwise stated. Numeric data will be reported at the precision collected on the eCRF. The reported precision from non eCRF sources will follow the IDSL statistical principles but may be adjusted to a clinically interpretable number of DP's. 	
Planned and Actual Time	

 Reporting for tables, figures and formal statistical analyses: 
 Planned time relative to dosing will be used in figures, summaries, statistical analyses and calculation of any derived parameters, unless otherwise stated. The impact of any major deviation from the planned assessment times and/or scheduled visit days on the analyses and interpretation of the results will be assessed as appropriate. Reporting for Data Listings: 
 Planned and actual time relative to study drug dosing will be shown in listings (Refer to IDSL Statistical Principle 5.05.1). Unscheduled or unplanned readings will be presented within the participant's listings. 	
Unscheduled Visits	

 • Unscheduled visits will not be included in summary tables and/or figures. • All unscheduled visits will be included in listings. 	
Descriptive Summary Statistics	
Continuous Data	Refer to IDSL Statistical Principle 6.06.1
Categorical Data	N, n, frequency, %
Graphical Displays	

 • Refer to IDSL Statistical Principals 7.01 to 7.13. 	

15.5.3. Reporting Standards for Pharmacokinetic

Pharmacokinetic Concentration Data	
PC Windows Non-Linear (WNL) File	PC WNL file (CSV format) for the non-compartmental analysis by Clinical Pharmacology Modelling and Simulation function will be created according to PKOne standards. Note: Concentration values will be imputed as per GUI_51487.
Descriptive Summary Statistics, Graphical Displays and Listings	Refer to IDSL PK Display Standards. Refer to IDSL Statistical Principle 6.06.1. Note: Concentration values will be imputed as per GUI_51487 for descriptive summary statistics/analysis and summarized graphical displays only.
NONMEM/Pop PK File	Pop-PK file (CSV format) for the POP-PK analysis by Clinical Pharmacology Modelling and Simulation function will be created. Dataset specification will be detailed in a separate document.
NONMEM/PK/PD File	PK/PD file (CSV format) for the PK/PD analysis by Clinical Pharmacology Modelling and Simulation function will be created. Dataset specification will be detailed in a separate document.
Pharmacokinetic Parameter Derivation	
PK Parameter to be Derived by Programmer	The following PK parameters will be derived by the Programmer: None
Pharmacokinetic Parameter Data	
Is NQ impacted PK Parameters Rule Being Followed	Yes, refer to SOP_314000.
Descriptive Summary Statistics, Graphical Displays and Listings	Refer to IDSL PK Display Standards. Refer to PKOne.

15.6. Appendix 6: Derived and Transformed Data

15.6.1. General (Parts A and B)

Multiple Measurements at One Analysis Time Point

 • Mean of the measurements will be calculated and used in any derivation of summary statistics but if listed, all data will be presented. • Participants having both High and Low values for Normal Ranges at any post-baseline visit for safety parameters will be counted in both the High and Low categories of “Any visit post-baseline” row of related summary tables. This will also be applicable to relevant Potential Clinical Importance summary tables.
Study Day

 • Calculated as the number of days from Dose Date: 
 • Ref Date = Missing → Study Day = Missing • Ref Date < Dose Date → Study Day = Ref Date – Dose Date • Ref Date ≥ Dose Date → Study Day = Ref Date – Dose Date + 1

15.6.2. Study Population

Age

 • Only year of birth will be collected on the CRF and birth date will be presented in listings as ‘YYYY’. • GSK standard IDSL algorithms will be used for calculating age where birth date will be imputed as ‘30th June’ and then calculated based on the dose date.

15.6.3. Safety

ECG Parameters
RR Interval

 • If RR interval (msec) is not provided directly, then RR can be derived as: 
 ○ If QTcF is machine read, then: $RR = \left[\left(\frac{QT}{QTcF} \right)^3 \right] * 1000$ ○ If ECGs are manually read, the RR value preceding the measurement QT interval should be a collected value, then do not derive.
Corrected QT Intervals

 • When not entered directly in the eCRF, corrected QT intervals by Fridericia’s (QTcF) formulas will be calculated, in msec, depending on the availability of other measurements. • IF RR interval (msec) is provided then missing QTcF will be derived as: $QTcF = \frac{QT}{\sqrt[3]{\frac{RR}{1000}}}$
Laboratory parameters

 • If a laboratory value which is expected to have a numeric value for summary purposes, has a non-detectable level reported in the database, where the numeric value is missing, but typically a character

ECG Parameters

value starting with '<x' or '>x' (or indicated as less than x or greater than x in the comment field) is present, the number of significant digits in the observed values will be used to determine how much to add or subtract in order to impute the corresponding numeric value.

- Example 1: 2 Significant Digits → '< x' becomes $x - 0.01$
- Example 2: 1 Significant Digit → '> x' becomes $x + 0.1$
- Example 3: 0 Significant Digits → '< x' becomes $x - 1$

15.7. Appendix 7: Reporting Standards for Missing Data

15.7.1. Premature Withdrawals

Element	Reporting Detail
General	
 In both Parts A and B, participant study completion (i.e. as specified in the protocol) is defined as having completed all phases of the study including the last scheduled assessment shown in the SoA (Section 15.2). Withdrawn participants may be replaced in the study. All available data from participants who were withdrawn from the study will be listed and all available data will be included in summary tables and figures, unless otherwise specified. Withdrawal visits will be slotted as per Section 15.3 or will be summarised as withdrawal visits.

15.7.2. Handling of Missing Data

Element	Reporting Detail
General	
 Missing data occurs when any requested data is not provided, leading to blank fields on the collection instrument: 
 These data will be indicated using a "blank" in participant listing displays, unless all data for a specific visit are missing (in which case the data is excluded from the table). Answers such as "Not applicable" and "Not evaluable" are not considered to be missing data and should be displayed as such.

15.7.2.1. Handling of Missing and Partial Dates

Element	Reporting Detail
General	
 Partial dates will be displayed as captured in participant listing displays.
Adverse Events	
 In case of partial dates (i.e. day missing, only month and year present) recorded for AE start and end, the following conventions will be applied for calculating the time to onset and the duration of the event: 
 Missing Start Day: First of the month will be used unless this is before the start date of study treatment; in this case the study treatment start date will be used and hence the event is considered Treatment Emergent as per Appendix 4: Study Phases and Treatment Emergent Adverse Events. Missing Stop Day: Last day of the month will be used, unless this is after the stop date of study treatment; in this case the last contact date will be used. Completely missing start or end dates will remain missing, with no imputation applied. Consequently, time to onset and duration of such events will be missing.
Concomitant Medications/ Medical History	
 Partial dates for any concomitant medications recorded in the CRF will be imputed using the following convention: 
 If the partial date is a start date: '01' will be used for the day if the month is not missing, and '01-Jan' will be used if both month and day are missing. If the partial date is a stop date: '28/29/30/31' will be used for the day if the month is not missing, and '31-Dec' will be used if both month and day are missing. For medications recorded in the eCRF as prior medications, the earlier of this imputed date or the day before the treatment start date will be used.

Element	Reporting Detail
	

• The recorded partial date will be displayed in listings.

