9.2.1. Time Period and Frequency for Collecting AE and SAE Information

- All SAEs will be collected from consenting participants until the Follow-Up visit at the time point specified in the SoA (Section 2). However, any SAEs assessed as related to study participation (e.g. study intervention, protocol-mandated procedures, invasive tests, or change in existing therapy) or related to a GSK product will be recorded from the time a participant consents to participate in the study.
- All AEs will be collected from the start of intervention until the Follow-Up visit at the time points specified in the SoA (Section 2).
- Medical occurrences that begin before the start of study intervention but after obtaining informed consent will be recorded on the Medical History/Current Medical Conditions section of the CRF not the AE section. The exceptions are SAEs, which must be recorded in the CRF AE/SAE section.
- All SAEs will be recorded and reported to the sponsor or designee immediately and under no circumstance should this exceed 24 hours, as indicated in [Appendix 3](#). The investigator will submit any updated SAE data to the sponsor within 24 hours of it being available.
- Investigators are not obligated to actively seek AEs or SAEs after the conclusion of the study participation. However, if the investigator learns of any SAE, including a death, at any time after a participant has been discharged from the study, and he/she considers the event to be reasonably related to the study intervention or study participation, the investigator must promptly notify the sponsor.

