8.1. Adverse Events Analyses

The definition of an AE is detailed in Appendix 3 of the protocol.

Analyses of AEs will include those events that are Treatment Emergent as defined in Section 15.4.

Adverse events analyses including the analysis of adverse events (AEs), Serious (SAEs) and other significant AEs will be based on GSK Core Data Standards. The details of the planned displays are provided in [Appendix 12: List of Data Displays](#).

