15.2. Appendix 2: Schedule of Activities

15.2.1. Part A: Japanese and Caucasian Participants – IV dose

Procedure	Screening (up to 28 days before Dosing)	Day -1	Day 1 (Hours)							Days 3 – 85										Follow Up/Early Withdrawal (112 Days post dose) ³
			Pre-Dose	0 h ¹	1 h	2 h (end of infusion)	6 h	12 h	24 h	3 ₂	4 ₂	8	15	22	29	43	57	71	85	
Window			-60 min		±10 min	+30 min ⁴	±30 min	±30 min	±60 min			±1 d	±2 d	±2 d	±2 d	±3 d	±3 d	±3 d	±3 d	±7d
Informed Consent	X																			
Inclusion and Exclusion Criteria	X	X																		
Demography	X																			
Full physical examination including height and weight	X																			X
Medical history (includes substance usage)	X																			
Past and Current Medical Conditions	X																			

Procedure	Screening (up to 28 days before Dosing)	Day -1	Day 1 (Hours)							Days 3 – 85										Follow Up/Early Withdrawal (112 Days post dose) ³
			Pre-Dose	0 h ¹	1 h	2 h (end of infusion)	6 h	12 h	24 h	3 ₂	4 ₂	8	15	22	29	43	57	71	85	
Window			-60 min		±10 min	+30 min ⁴	±30 min	±30 min	±60 min			±1 d	±2 d	±2 d	±2 d	±3 d	±3 d	±3 d	±3 d	±7d
Serology (HIV, HBV, HCV, CMV, EBV, VZV)	X																			
TB screening (QuantiFERON ± PPD)	X																			
Breath Alcohol Screen	X	X																		
Urine Drug Screen	X	X																		
Haematology & Clinical Chemistry	X	X						X	X		X	X		X	X	X		X	X	
Urinalysis	X	X						X	X		X	X		X	X	X		X	X	
12-Lead ECG ⁵	X		X				X		X									X	X	
Vital Signs ⁶	X	X	X		X	X	X	X	X	X	X	X	X	X	X	X	X	X	X	X

Procedure	Screening (up to 28 days before Dosing)	Day -1	Day 1 (Hours)							Days 3 – 85										Follow Up/Early Withdrawal (112 Days post dose) ³	
			Pre-Dose	0 h ¹	1 h	2 h (end of infusion)	6 h	12 h	24 h	3 ₂	4 ₂	8	15	22	29	43	57	71	85		
Window			-60 min		±10 min	+30 min ⁴	±30 min	±30 min	±60 min			±1 d	±2 d	±2 d	±2 d	±3 d	±3 d	±3 d	±3 d	±7d	
Randomization		X																			
IMP Administration				←-----→																	
Resident in unit			←-----→																		
Local Tolerability			X			X	X	X	X												
sLAG3 concentrations			X		X	X	X	X	X	X	X	X	X	X	X	X	X	X	X	X	X
PK			X		X	X ⁷	X	X	X	X	X	X	X	X	X	X	X	X	X	X	X
Immunogenicity			X											X		X		X		X	X
LAG3 ⁺ Cell Depletion and Immunophenotyping			X				X		X		X	X	X		X	X	X		X		X
Genetic Sample ⁸			X																		
AE/ SAE Review	SAEs collected from signing of informed consent form; AEs collected continuously from time of first dose.																				

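### SAP 15.7.2.1 and 15.4.1 put an adverse event imputed to the dosing date in opposite study phases, and the missing-stop-day rule does not suit a single dose

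*SAP*

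**What the plan says.** SAP 15.7.2.1 deals with AE dates that lack the day. A missing start day becomes the first of the month unless that falls before treatment start, and then "in this case the study treatment start date will be used and hence the event is considered Treatment Emergent as per Appendix 4". A missing stop day becomes the last day of the month, "unless this is after the stop date of study treatment; in this case the last contact date will be used".

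Appendix 4 begins in SAP 15.4.1: "Assessments and events will be classified according to the time of occurrence relative to the dose". Its table has two rows. A date/time less than or equal to treatment start is Pre-Treatment, and one strictly greater is Treatment Emergent. SAP 15.4.2 applies the table to AE start date/time: "Adverse Events will be flagged as Treatment Emergent as described in the table in Section" 15.4.1. SAP 8.1 makes the flag decisive: "Analyses of AEs will include those events that are Treatment Emergent as defined in Section 15.4".

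On collection, the schedule in SAP 15.2.1 states "SAEs collected from signing of informed consent form; AEs collected continuously from time of first dose", with screening up to 28 days before dosing. Protocol 9.2.1 sends other pre-dose occurrences to medical history: "The exceptions are SAEs, which must be recorded in the CRF AE/SAE section". SAP 2.3 gives one dose, on Day 1, in each part.

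**The concern.** An imputed start equal to treatment start meets the table's Pre-Treatment condition. The conclusion in 15.7.2.1 therefore does not follow from the appendix it cites. A programmer working from the table would leave the event out of the AE summaries, and one working from 15.7.2.1 would include it.

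Two further faults sit in the same section. The start rule puts no lower limit on the recorded month, so an SAE known to have begun in a month before dosing is also moved to the dosing date and called Treatment Emergent. The stop rule compares month-end with the end of treatment. In a single-dose study that is Day 1, so the condition is met almost every time and last contact replaces a month that was actually recorded.

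AEs are a primary endpoint, and the active groups have 6 participants (each Part A stratum) or 8 (each Part B dose). One participant wrongly included or left out moves a displayed rate by 1/6 = 16.7 or 1/8 = 12.5 percentage points.

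**Working it through.** The plan states no figure to reproduce here. The check applies the rules to calendar dates. The years 2019-2020 (731 dosing dates) were chosen only to cover every month length.

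**Class of the imputed start.** The SAP gives no clock time for an imputed date, so four readings were tried against the 15.4.1 table:

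| Reading of the imputed start | Class |
|---|---|
| Compare dates only | Pre-Treatment |
| Set to the dose date and time | Pre-Treatment |
| Dosing date at 00:00 | Pre-Treatment |
| Dosing date at 23:59 | Treatment Emergent |

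Only a clock time after the dose, which the SAP does not specify, yields the class that 15.7.2.1 asserts.

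**When the conflict arises.** For a start recorded only as the dosing month, it arises when the first of the month is before the dosing date: 707/731 = 96.7%. On the other 24 dates dosing is on the first. The imputed start still equals the dosing date and the table gives Pre-Treatment, but the sentence in 15.7.2.1 is not invoked, so nothing says otherwise.

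**Pre-dose SAEs.** Dosing date minus 28 days falls in an earlier calendar month for 672/731 = 91.9% of dosing dates. For these, an SAE during screening can be recorded in a month that lies wholly before dosing and still be moved to the dosing date.

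**Stop rule: trigger.** For a stop in the dosing month, month-end is after the dosing date on 707/731 dates (all except dosing on the last day of a month). For any later month it is after the dosing date on 731/731. Taking every dosing date in one year with every possible stop day from dosing to 112 days later gives 365 × 113 = 41,245 combinations. The trigger is met in 41,233 of them (99.97%).

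**Stop rule: size.** Excess = last contact − end of recorded month, with last contact at dosing + 112 days. The final column takes in the ±7-day visit window, i.e. last contact from 105 to 119 days.

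| Recorded stop month | Excess at 112 days | Over 105 to 119 days |
|---|---|---|
| Dosing month | 82-111 days | 75-118 |
| Next month | 51-84 | 44-91 |
| Second month after | 21-53 | 14-60 |
| Third month after (495/731 dates at 112 days) | 1-23 | 1-30 |

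The last row covers only dates on which last contact falls in a later month than the recorded one. When last contact is in the recorded month, the rule gives the same date as the earlier of month-end and last contact.

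Over the 41,245 combinations, the imputed stop lies outside the recorded month in 86%. It overstates the true stop by 56 days on average (maximum 112). Taking the earlier of month-end and last contact cuts this to 13 days (maximum 30). These averages treat dosing dates and stop days as evenly spread, so they illustrate the rule and do not predict the trial.

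**Illustration.** Dose and AE start on 12 June 2019, true stop 14 June with the day missing. True duration is 3 days. Last contact is 2 October, so the SAP rule gives 113 days. The earlier of month-end and last contact gives 19 days.

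**The case against.** The strongest reply is that 15.7.2.1 is the more specific rule and states its outcome in words. The table compares date/time with date/time, and an imputed date has no time, so the sentence can be read as filling a gap. Non-serious AEs are collected only from dosing, so the intended class is not in doubt. This is right about intent. But the sentence cites Appendix 4 as its authority and does not override it, while 15.4.2 and 8.1 send the flag back to the table.

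The two start-date errors are also alternatives. If the table governs, the earlier-month SAE correctly stays Pre-Treatment and partial-date AEs in the dosing month are lost. If the sentence governs, those AEs are correctly kept and the earlier-month SAE is wrong. That stands, yet each reading leaves one class of partial date misplaced.

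The SAE case is remote. It needs a healthy volunteer with an SAE in screening who is still eligible and dosed, and whose start is known only to the month although SAEs are reported within 24 hours. The 91.9% is calendar arithmetic, not a misclassification rate. The stop rule changes no AE count, no planned AE table title reports duration, and listings show partial dates as captured. All of this stands and limits the severity.

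Finally, a single override sentence would settle the main conflict without moving the boundary for fully dated AEs. That would also work, but it would leave the earlier-month SAE and the stop rule to be corrected separately.

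**Conclusion.** The point holds, as a minor one. The start rule and the table it relies on give opposite classes when an imputed start equals treatment start. The start rule also reaches back to months before dosing, and the stop rule overrides the recorded month almost whenever it is used. These are stated rules that give wrong results, not missing detail.

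The percentages are conditional on a partial date having occurred. The documents give no frequency for that, and few are likely in a resident single-dose study. The stop-date ranges assume completion to the Day 112 follow-up; early withdrawal gives smaller gaps. Listings 15 and 48 show all AEs, so a misplaced event could be found there.

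**What to change.** In SAP 15.4.1, define Treatment Emergent for AEs as a start at or after treatment start and Pre-Treatment as strictly before, comparing on date only when the start is imputed.

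In SAP 15.7.2.1:

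- Impute a missing start day to the dosing date only when the recorded month and year are those of dosing.
- Use the first of the month for later months.
- Leave a start recorded in an earlier month, which can arise for SAEs collected from consent, as Pre-Treatment.
- Set a missing stop day to the earlier of the last day of the recorded month and the last contact date.

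The same edit should say how a full dosing-day date without a clock time is classed, since the date-only comparison above covers imputed starts only.

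The cost is a few sentences in the SAP and a small derivation change before unblinding. The downside is that an event at the exact dosing time, or a pre-dose SAE with a partial date in the dosing month, will count as Treatment Emergent.
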